## Rationale:

Basal Cell Carcinoma (BCC) is the most common malignancy in humans. Its incidence is continuously increasing. The head and neck areas are most commonly affected due to their increased lifetime exposure to sun compared to other body parts. BCC is often treated by surgical excision which has high cure rate compared to other treatment modalities, but leaves a visible scar which can affect the quality of life of the patient, depending on the location and size of the excision. Mohs Micrographic Surgery (MMS) was developed to minimize the size of the surgical excision whilst maintaining very high cure rate. The main drawback of MMS is that repeated surgery procedures may be required to eliminate all of the tumour using specialist resources located at the clinic.

Optical Coherence Tomography (OCT) allows non-invasive in-vivo imaging of superficial skin lesions. It is in routine clinical use for diagnosis of BCCs, and the diagnostic sensitivity and specificity is well established in published multi-centre trials. A further potential application of OCT is the pre-surgical mapping of the lateral margins of BCC. If the margins of a BCC were accurately known prior to commencing an MMS treatment, the treatment could be performed much more quickly, resulting in shorter patient stays and more efficient use of surgical and operating room resources. Previously published research has already shown that OCT mapping of BCC margins is more accurate than clinical assessment; the objective of the present study is to demonstrate that pre-surgical mapping of BCC margins with OCT is also more efficient.

## Hypothesis:

That presurgical margin mapping of BCCs with OCT results in a reduction of the number of MMS surgery stages to < 1.4 without adversely impacting clinical outcome.

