## Objectives:

Primary Objective:

- Show that the average number of MMS stages by using pre-surgical margin mapping with OCT is  $< 1.4$

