#### Secondary Objectives:

- Validate that the reduction in MMS stages by use of OCT mapping does not result in an increase in the size of the surgical defect
- Show that the average time taken to perform OCT margin mapping is  $< 5$  minutes for lesions of area  $< 2 \text{ cm}^2$

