##### Final Observations

8. Finally, prior to closure of the wound, the size of the surgical defect of all lesions is measured by tracing the extent on squared transparent paper and also photographed with a scale. The subtype of the BCC from the Mohs histology is recorded (nodular / superficial / infiltrative / other)

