#### Start and Duration

The study is designed for 2 years starting immediately after approval by ethics committee. Recruitment will be 2 patients per week.

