##### 2. Secondary Objectives

- The area of lesions will be obtained from the tracings of the mark obtained by placing a transparent TegaDerm™ adhesive dressing over the mark, removing it (with ink transferred) and pasting on to squared graph paper and then counting the number of squares inside the traced borders.

- The area of the surgical defect will be obtained by placing OpSite™ squared adhesive dressing over the defect prior to commencement of repair, using an ink marker to trace the defect on the dressing, and then counting the number of squares inside the traced borders.
  
- The following will be calculated
  - i. The mean, r.m.s. and maximum difference between the area of the OCT map made by Mohs surgeon and the area of the OCT map made by Observer #1, for lesions in the OCT Arm
  - ii. The mean, r.m.s. and maximum difference of the area of the OCT map made by Observer #1 and the area of final surgical lesion in the Control Arm.

From (i) we will quantify the difference between the Mohs surgeon and Observer's OCT mapping, and whether the Mohs surgeon's margins are consistently smaller or larger.

From (ii) we will determine whether the Observer's margins are smaller or larger than the final surgical lesion, and from (i) then show whether the surgeon's margin are expected to be smaller than the final surgical lesion, and by how much.

Figure 2. Schematic of process showing the areas.

Finally, the average time taken to OCT map lesions will be calculated:

- For all lesions
- For lesions, divided into the following subcategories by clinically visible lesion size:
  - o < 2.0 cm^2
  - o 2.0 – 4.0 cm^2
  - o > 4.0 cm^2

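### The hypothesis claims no harm to clinical outcome, but the only safeguard measured is surgical defect area, and the listed calculations do not compare it between the arms

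*Protocol*

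**What the plan says.** The Protocol's Hypothesis has two halves: a mean stage count below 1.4, and that this is achieved "without adversely impacting clinical outcome". Nothing in the document defines clinical outcome.

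The primary objective covers the first half only ("Show that the average number of MMS stages by using pre-surgical margin mapping with OCT is" below 1.4). The nearest thing to the second half is the first secondary objective, that the reduction in stages "does not result in an increase in the size of the surgical defect". Under Final Observations, "the size of the surgical defect of all lesions is measured", in both arms and before closure.

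The Rationale says that Mohs surgery was developed to "minimize the size of the surgical excision whilst maintaining very high cure rate".

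Under Data and Analysis, Secondary Objectives, two area calculations are listed:

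- Calculation (i) takes the difference between the surgeon's OCT map and "the area of the OCT map made by Observer #1, for lesions in the OCT Arm".
- Calculation (ii) takes the difference between the OCT map made by "Observer #1 and the area of final surgical lesion in the Control Arm".

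**The concern.** The hypothesis promises more than the trial observes. If the mean stage count falls below 1.4, a report that repeats the hypothesis as confirmed would carry a statement about clinical outcome for which the only evidence is the area of tissue removed.

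That narrower evidence is also not set out as a randomised comparison. The trial randomises 100 patients to each arm and measures the defect in all of them. Yet neither listed calculation uses the defects of the OCT Arm.

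**Working it through.** The plan gives no figure for this half of the hypothesis to reproduce. Its 83 patients and its 1.4 threshold concern the stage count only. The check is therefore a comparison of passages, with some algebra on the area calculations.

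**Step 1. What is observed, and when.**

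| Variable | Where in the Protocol | When, and in whom |
|---|---|---|
| Clinically assessed lesion size | Study-related interventions; Data and Analysis 2 | before surgery |
| Observer #1's OCT map area and mapping time | Initial Steps | before randomisation, all patients |
| Surgeon's OCT map area and mapping time | OCT Arm | before excision, OCT Arm only |
| Number of stages | OCT Arm; Data and Analysis 1 | during surgery, both arms |
| Final defect area | Final Observations | before closure, both arms |
| BCC subtype | Final Observations | from the Mohs histology |
| First-stage margin status, anatomical location | Data and Analysis 3 | OCT Arm lesions needing more than one stage |

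No row is a recurrence, cure, complication or patient-reported outcome, and none is observed after closure.

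**Step 2. Can defect area stand for clinical outcome?** The Rationale sets Mohs surgery two aims, a small excision and a high cure rate. Defect area speaks to the first and says nothing about the second.

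**Step 3. Do calculations (i) and (ii) test defect area between arms?** Write M1 for Observer #1's map area, M2 for the surgeon's map area, D for the final defect area and E for a mean. The Protocol does not fix the sign in (ii); I take map minus defect.

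- (i) estimates E(M2 − M1) in the OCT Arm.
- (ii) estimates E(M1 − D) in the Control Arm.
- M1 is measured before randomisation, so its expected value is the same in both arms. The two therefore chain to: (i) + (ii) = E(M2, OCT Arm) − E(D, Control Arm).
- The secondary objective needs: E(D, OCT Arm) − E(D, Control Arm).
- Needed minus chained = E(D − M2) in the OCT Arm.

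The remainder is the amount by which the final defect in the OCT Arm exceeds the surgeon's own map. Neither calculation estimates it. If it is positive, the chain understates the defect difference by exactly that amount.

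It cannot be taken as nil by design. The Case Number Estimation assumes a true mean of 1.2 stages with OCT. That is 1.2 − 1 = 0.2 further stages per patient, or 0.2 × 100 = 20 further stages across the arm, all taken after the map was drawn. Stages taken for depth alone might add no area; the others would.

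**Step 4. Does Avoiding Bias close the gap?** That section also compares Observer #1's map with the final defect for all lesions. Its stated purpose is to confirm that mapped borders do not exceed the defect, which is again map against defect. Split by arm and contrasted, the same data would answer the question, because E(D − M1, OCT Arm) − E(D − M1, Control Arm) equals the needed difference under randomisation. So the data exist, but the Protocol does not set out the contrast.

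**The case against.** The strongest reply is that the secondary objective on defect size is how the Protocol puts the second half of the hypothesis into practice. There is a reason for that choice. OCT alters only the first-stage estimate; both arms then have Mohs surgery, in which repeat stages serve to remove remaining tumour. The harm the Protocol identifies is unnecessary removal of healthy tissue, and it measures that. The Rationale also ties excision size to scarring and quality of life. The formal objectives claim nothing about cure.

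Much of this stands. A reader might infer that the trial measures no clinical outcome at all, and the document does not support that: defect area is a patient-relevant result recorded in both arms. What does not follow is that defect area covers everything in an undefined and broader phrase, when the Rationale itself names cure separately.

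A second reply is that a statistical analysis plan, not at hand, may contain the between-arm comparison. It may, and then only the Protocol's list would need aligning. It could not supply outcomes that are never collected, so the wording of the hypothesis would remain at fault.

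**Conclusion.** Wrong as written. The second half of the hypothesis cannot be concluded, because no recurrence, cure or complication data and no observation after closure are planned. A conclusion on defect area is within reach, but calculations (i) and (ii) do not deliver it. The primary objective is unaffected. This rests on reading every objective, procedure and analysis section of the Protocol, and on randomisation balancing Observer #1's map area in expectation.

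Two further inferences are tempting and go too far:

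- **That the timetable rules out follow-up.** "Recruitment will be 2 patients per week", so 200 patients take 200 / 2 = 100 of about 104 weeks. That leaves almost nothing for the last patients, but those enrolled early could be followed for well over a year. The document shows that follow-up is not planned, not that it is impossible.
- **That histological clearance is judged by an unblinded surgeon.** The document does not say who reads the histology or whether that reader knows the arm.

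Nor does the point show that OCT mapping worsens cure. The Protocol gives no recurrence rate from which the size of any such effect could be worked out.

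**What to change.** 1. In the Hypothesis, replace the phrase on clinical outcome with: *without increasing the area of the surgical defect compared with standard MMS*.
2. Under Data and Analysis, Secondary Objectives, add a comparison of final defect area between the OCT Arm and the Control Arm, with a 95% confidence interval, adjusted for Observer #1's mapped area. That area is measured before randomisation in every patient, so it is a sound covariate. A statement of no increase should rest on the upper limit of the interval, not on the absence of a significant difference.
3. State that the trial does not assess recurrence, cure or complications, and limit the conclusion in the report accordingly.

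The cost is a narrower headline claim and one extra analysis. Both areas are already collected in both arms, so no visit, staff or patient is added. Calculations (i) and (ii) can stay as checks on how the surgeon maps.

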## Objectives:

Primary Objective:

- Show that the average number of MMS stages by using pre-surgical margin mapping with OCT is  $< 1.4$

#### Secondary Objectives:

- Validate that the reduction in MMS stages by use of OCT mapping does not result in an increase in the size of the surgical defect
- Show that the average time taken to perform OCT margin mapping is  $< 5$  minutes for lesions of area  $< 2 \text{ cm}^2$

#### Tertiary Objectives:

- For those lesions for which OCT margin mapping did not result in a single stage operation:
  - o Determine the proportion of each BCC subtype (nodular, superficial, or infiltrative BCC)
  - o Determine the proportion for which the first surgery stage had margins that were not clear (i) laterally (ii) in depth
  - o Determine whether anatomical location is a factor

#### Population:

##### Inclusion criteria:

- 200 patients with biopsy-proven BCCs who have been referred for MMS
- Adults  $> 18$  years of age
- Informed consent

##### Exclusion criteria:

- Patients with BCCs larger than  $6 \text{ cm}^2$

#### Study Design:

Interventional Randomised Controlled Trial (RCT)

Previously published research [1-5] has shown that, under controlled conditions, OCT mapping of BCC margins is more accurate than clinical assessment and so is expected to produce a reduction in the number of MMS stages. However, the efficiency of the technique, in terms of the reduction in MMS stages versus the additional time required to OCT map the lesion, has not been quantified.

This RCT is designed to quantify the improvement in efficiency, and validate that it is more efficient than standard MMS. The study comprises two Arms, one is the OCT arm and one is the Control Arm. In the OCT Arm, OCT is used to map the tumour margins and the resulting number of MMS stages is recorded.

In the Control Arm, standard MMS is performed.

In order to be completely sure that the reduction in MMS stages using OCT has not been obtained at the cost of increasing the amount of tissue excised, all tumours are also mapped at initial consultation, prior to randomization, by a second observer. See Figure 1 Outline Protocol below.

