##### A. OCT Arm

5. Observer #2 (the Mohs surgeon) maps the extent of the BCC tumour using OCT. The time taken, size and shape of the mapped border is recorded.
6. The Mohs surgeon performs Mohs surgery using the marked OCT mapped borders as the first stage estimate. The number of MMS stages is recorded.

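### The protocol promises to prove OCT mapping more efficient, but lists no surgical times with which to weigh stages saved against mapping minutes added

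*Protocol*

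**What the plan says.** The Rationale sets the overall aim: "the objective of the present study is to demonstrate that pre-surgical mapping of BCC margins with OCT is also more efficient". It motivates that aim by time and resources, saying that with accurately known margins "the treatment could be performed much more quickly, resulting in shorter patient stays and more efficient use of surgical and operating room resources". Study Design repeats the claim more firmly, "This RCT is designed to quantify the improvement in efficiency, and validate that it is more efficient than standard MMS", and says what efficiency means here: "in terms of the reduction in MMS stages versus the additional time required to OCT map the lesion".

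The data listed for this purpose are:

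- **Stages.** In Figure 1, OCT Arm, "The number of MMS stages is recorded". Data and Analysis, Primary Objective, gives the mean per arm with 95% limits for each arm, so the count is evidently taken in the control arm too.
- **Mapping time.** It is recorded for Observer #1 before randomization and for the surgeon in the OCT arm. It is averaged overall and by lesion size under Data and Analysis, Secondary Objectives. The target is under Secondary Objectives: "Show that the average time taken to perform OCT margin mapping is" under 5 minutes, for lesions below 2 cm².

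The Control Arm step in Figure 1 lists no time. Under Final Observations, "the size of the surgical defect of all lesions is measured by tracing the extent on squared transparent paper", and the subtype is noted. The remaining analyses concern areas, subtype, margin status and anatomical site. No stage, procedure, operating-room or stay duration is listed for either arm.

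**The concern.** Efficiency as the protocol frames it has a gain side and a cost side. The gain is counted in stages and the cost in minutes. To say that one exceeds the other, a stage must be expressed in minutes, and nothing listed for collection does that.

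An analysis plan could bring in an assumed or published stage duration. The answer would then rest on that outside figure and not on the surgery done in this trial. No analysis plan can analyse times that were not recorded.

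At stake is the headline conclusion. Suppose the trial meets both the stage objective (mean below 1.4) and the mapping-time objective (mean below 5 minutes for small lesions). It could then report fewer stages (if the control mean is higher, as planned) and a short mapping time. It could not, from its own data, report that OCT mapping saves time overall.

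**Working it through.** **The plan's own figures.** The protocol gives no figure for net efficiency, so there is none to reproduce. Its one calculated figure, 83 patients in the OCT arm, concerns the stage count only. No standard deviation (SD) or power is stated for it. A one-sample normal approximation with a difference of 0.2 and one-sided 0.025 implies an SD of about 0.65 at 80% power or 0.56 at 90%. This point does not depend on that figure.

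**Inputs**

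- Control mean stages C = 1.5 to 1.7 (Case Number Estimation).
- OCT mean stages O = 1.2 (Case Number Estimation); success criterion below 1.4 (Primary Objective).
- Mapping time m = 5 minutes. This is the upper limit of the target for lesions below 2 cm², used here as if it were the mean over all lesions (assumption).
- Minutes per stage t: not in the protocol.

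**Formulae.** Net time saved per patient = (C − O) × t − m. The break-even stage length is t = m / (C − O).

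**What trial data alone can give.** The ratio m / (C − O), in mapping minutes per stage avoided, needs only the planned data.

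| C | O | Stages saved | Per 1 minute of mapping | At 5 minutes of mapping |
|---|---|---|---|---|
| 1.5 | 1.2 | 0.3 | 1/0.3 = 3.3 | 5/0.3 = 16.7 |
| 1.7 | 1.2 | 0.5 | 1/0.5 = 2.0 | 5/0.5 = 10.0 |
| 1.5 | just under 1.4 | about 0.1 | about 10 | about 50 |
| 1.7 | just under 1.4 | about 0.3 | about 3.3 | about 16.7 |

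The last two columns are also the stage lengths, in minutes, above which OCT saves time. Reading them as a gain or a loss needs t.

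**Range over an assumed t of 10 to 60 minutes, m = 5**

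- 1.5 against 1.2: 0.3×10 − 5 = −2 to 0.3×60 − 5 = +13 minutes.
- 1.7 against 1.2: 0.5×10 − 5 = 0 to 0.5×60 − 5 = +25 minutes.
- 1.5 against just under 1.4: 0.1×10 − 5 = −4 to 0.1×60 − 5 = +1 minute.

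The sign can change within this range, and the quantity that decides it is not listed for collection.

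**What recording stage times would yield**

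- Stage records: 100×1.2 + 100×1.5 = 270, to 100×1.2 + 100×1.7 = 290.
- 95% half-width of a between-arm difference in time, 100 per arm: 1.96 × SD × √(2/100) = 0.277 × SD. This is 8.3 minutes if the SD is 30 and 16.6 if it is 60 (SDs assumed).
- Second and later stages: 100×0.2 + 100×0.5 = 70, to 100×0.2 + 100×0.7 = 90. The half-width of their mean duration is 1.96 × SD / √n. With an SD of 15 it is 3.5 minutes (n = 70) or 3.1 (n = 90); with an SD of 30 it is 7.0 or 6.2. These figures treat stages as independent. Third and later stages share a patient with a second stage, so the true interval may be wider.

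**The case against.** The strongest reply is that net time is not the protocol's own yardstick. Study Design sets stage reduction against mapping time, and both are planned as trial data. Mapping minutes per stage avoided is an ordinary incremental ratio, and how to form it can be left to an analysis plan. The language about quicker treatment in the Rationale is conditional and serves as motivation. The Hypothesis and Objectives promise no saving in surgical time, stay or theatre use, and every listed objective can be answered.

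Much of this stands. A reader might infer that the trial cannot quantify efficiency at all, and that would be wrong: the two components and their ratio are obtainable. What the ratio cannot do is validate superiority. A finding of, say, 17 mapping minutes per stage avoided is a gain if a stage takes longer than that and a loss if it takes less. The words about demonstrating and validating greater efficiency, in the Rationale and in Study Design, go beyond what the ratio supports.

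Two further cautions stand. The 5-minute figure is the top of a target range; if the target is met, mean mapping time for small lesions is shorter and the threshold falls. Recording times may also still leave the matter open, since a half-width of 8 to 17 minutes could cover zero for a modest saving.

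**Conclusion.** The concern holds in limited form. The stated aim of showing greater efficiency goes further than the listed data, because a stage saved cannot be turned into minutes from this trial. At the planning values and 5 minutes of mapping, the conclusion turns on whether a stage exceeds about 17 minutes (control mean 1.5) or 10 minutes (control mean 1.7).

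These thresholds assume that 5 minutes is the average mapping time, that a saved stage lasts as long as the stage length used, and that the OCT-guided first stage takes no longer than a standard one. They also take the protocol's list of recorded data as complete.

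Three stronger readings are not supported:

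- **That OCT mapping saves no time.** The protocol gives no stage duration, and a net saving may well exist.
- **That the primary endpoint or sample size is undermined.** Neither depends on this point.
- **That the balance is worse for larger lesions.** The mapping target stops at 2 cm², while the only size exclusion is "Patients with BCCs larger than" 6 cm². But neither the mapping time nor the stage saving for larger lesions is given. Dividing an assumed large-lesion mapping time by the all-lesion stage saving would therefore mean little.

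**What to change.** Record the start and end clock times of each MMS stage in both arms. Report the between-arm difference with a 95% confidence interval, as estimation and not as a powered test, for two separately defined quantities:

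- **Active time:** the surgeon's mapping time (OCT arm) plus stage times, without waiting. This speaks to surgical resources.
- **Elapsed time:** from the start of the surgeon's mapping (OCT arm) or of the first stage (control arm) to the end of the last stage, including waiting. This speaks to patient stay.

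Also report the mean duration of second and later stages, allowing for clustering within patient, since these are the stages OCT would avoid. Observer #1's mapping is a bias check done in all patients and should stay out of both totals.

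The cost is small: about 270 to 290 stage records at the planning values, with no added visit or procedure. The downside is some data-collection burden and an interval that may not resolve a small saving.

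If times will not be recorded, replace *more efficient* in the Rationale and Study Design with *requires fewer stages, with mapping time reported*. That costs nothing.
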